**Intermittently Scanned CGM Versus Usual Care With Diabetes Education and Feedback,
in Adults with Non-Insulin Dependent Type 2 Diabetes (iCUDE)
A Randomized Trial**

Short Title: isCGM With Education and Feedback for Non-Insulin Dependent Type 2 Diabetes

Protocol Version (2.3): September 12, 2022

Primary Investigator: [name]

Lead Statistician:

To be determined

Co-investigators:

[name]

[name]

Trial Coordinating Centre:

EPICORE Centre

[name]

University of Alberta,

Edmonton, Alberta, Canada

[figure not shown]
STUDY SYNOPSIS

Title	Intermittently Scanned CGM Versus Usual Care With Diabetes Education and Feedback, in Adults with Type 2 Diabetes (iCUDE): A Randomized Trial
Investigator(s)/center/study location	Edmonton, Alberta
Study Objectives	This trial will examine the effectiveness of intermittently-scanned continuous glucose monitoring (isCGM) when applied on an episodic basis and combined with diabetes education / feedback, in adults with type 2 diabetes on non-insulin therapy.
Study Design	The trial is an investigator-initiated prospective, single-center, open-label, randomized controlled trial.
Inclusion criteria:	
 1. Age ≥ 18 years with type 2 diabetes. 2. HbA1c $> 7.0\%$ within the last 6 months. 3. Non-insulin therapy. 4. Able to attend two in-person study visits. 5. English-speaking. 6. Community-dwelling. 7. In possession of a cell phone capable of accessing the internet and receiving FreeStyle Libre 2 sensor readings 8. Has a primary care provider who has been in contact with the patient for diabetes in the last 12 months.
Exclusion criteria:	
 1. Type 1 diabetes or diabetes clearly identified as having monogenetic etiology (e.g.: MODY). 2. Steroid-induced diabetes if steroid use is on-going or most recently taken within the last 3 months. 3. Pregnancy, plans to become pregnant within 6 months, or breast-feeding 4. Any use of insulin in the previous year. 5. Current or previous use of isCGM or rtCGM. 6. Cognitive dysfunction (SPMSQ score ≥ 5). 7. Symptoms of acute metabolic decompensation (extreme thirst, high urinary output, and weight loss, accompanied by acute fatigue or dyspnea). 8. Any terminal condition that would limit life expectancy to < 1 year. 9. Inability or refusal to use isCGM (e.g.: afraid of the device). 10. Inability or refusal to be reached by telephone. 11. Concurrent participation in another diabetes-related trial. 12. Has not already received two doses of a Health Canada-approved vaccine against SARS-CoV-2.
Evaluation criteria	
Primary Outcome: Change in glycated hemoglobin (HbA1c) at 3 months compared to baseline.
 
Secondary Outcomes: Feasibility of recruitment Blood pressure, body weight, waist circumference, and patient-reported outcomes, measured as change in continuous score at 3 months compared to baseline on validated instruments of:
 
 • Diabetes treatment satisfaction • Diabetes self-management empowerment • Diabetes-related distress • Diet • Physical activity

	Safety Outcomes: Any reported adverse events, major adverse events – hospitalization or ED visits. isCGM-related reactions (e.g.: skin reactions).
Treatment	Following informed consent, eligible adults will be randomly allocated to isCGM + education and feedback with a certified diabetes educator (CDE) or enhanced usual care with education and feedback using a 1:1 allocation ratio. The intervention (isCGM or enhanced usual care) will last 6-8 weeks. Those in the isCGM arm are free during the intervention or afterwards to obtain or fund their own supplemental isCGM sensors.
Randomization	Patients will be randomly assigned using a REDCAP based randomization system using variable block size. The computer-generated allocation table would be generated in a formal and secure manner.
Sample size	A target sample of 100 patients was chosen based on funding constraints, power / sample size considerations, and expected loss to follow-up of 20-30%. The minimum number of trial completers required to have 80% power to detect an HbA1c difference of 0.5% is 80.
Follow-up	Follow-up (week 5-6) CDE virtual education and feed-back session. 12-week bloodwork encounter at outpatient lab. 12-week in-person study encounter to complete study measurements. After conclusion of the 12 week trial period: Post-trial qualitative interviews with select consenting participants. Post-trial administrative linkage to examine outcomes at 24-52 weeks from randomization – no direct participant involvement.

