10. STUDY OUTCOMES AND VARIABLES

Case report forms are provided in Appendix 5. These will be translated into electronic documents to be completed by participants via a password protected webportal (EpiCore).

Primary Outcome:

- Change in HbA1c at 12 weeks compared to baseline.

Secondary Outcomes:

- Feasibility of recruitment
 - Participant referral, screening, and randomization rates over time
 - Reasons for inclusion / exclusion of all participants referred.
- Change in scores at 6 and 12 weeks compared to baseline, on the patient-reported outcomes shown in Table 1, below.
- isCGM participants only – change in time-in-target range, coefficient of variation, and glucose management indicator at 12 weeks compared to baseline.

Table 1: Patient-Reported Outcomes

Outcome	Instrument	Number of items
Diabetes treatment satisfaction – Status score	Diabetes Treatment Satisfaction Questionnaire (DTSQs) ³⁷ (weeks 6 and 12)	8
Diabetes treatment satisfaction – Change score	Diabetes Treatment Satisfaction Questionnaire (DTSQc) (week 6 only)	
Self-management empowerment	Diabetes Empowerment Scale – Short Form (DES-SF) ³⁸ (weeks 6 and 12)	8
Diabetes-related distress	Problem Areas in Diabetes (PAID) Questionnaire ³⁹	20
Diet	UK Diabetes and Diet Questionnaire (UKDDQ) ⁴⁰ (weeks 6 and 12)	25
Physical activity	International Physical Activity Questionnaire (IPAQ) short form ^{41,42} (weeks 6 and 12)	7
Health status	Euroqol EQ-5D-5L (weeks 6 and 12)	5

* In addition to collection at baseline.

Safety outcomes at 12 weeks:

- Any adverse events (serious and non-serious) occurring from baseline to 12 weeks will be identified and tracked at the 12 week study visit by patient interview, and reviewed

by study investigators to determine whether clinically attributable to diabetes, diabetes management, or isCGM. isCGM issues (e.g.: skin reactions) will be specifically sought.

- Emergency department visits or hospital admission for any reason, identified from patient interview and from NetCare review.

Qualitative Outcomes: Semi-structured interviews will undergo thematic analysis using constant comparative methods. The starting point will be the participant and provider experience with isCGM or enhanced usual care, with a particular focus on barriers and enablers of effectiveness (see Appendix 6, interview guides). Semi-structured interviews will take place for participants after trial completion (from 12-24 weeks).

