13. TREATMENT-EMERGENT ADVERSE EVENTS

Included participants belong to a population (adults with type 2 diabetes and are not on insulin) that does not typically experience hypoglycemia, and do not typically measure their glucose levels. No serious adverse events are expected. However, this protocol has several features to identify unexpected adverse events during the study.

- All emergency department visits and hospitalizations occurring from randomization to week 12 will be reviewed and adjudicated (see Appendix 5.6 for adverse event reporting forms) by study investigators. If a serious adverse event occurred because of the trial or trial intervention, study protocols will be reviewed and amended to mitigate the harm.
- We are performing in-person visits with participants to measure BP and weight. There is the possibility that we detect extremely abnormal physical parameters (e.g.: severe hypertension $\geq 180/110$ mmHg, severe hypotension SBP < 90 mmHg). A study investigator will be paged if a result this extreme is detected and the participant will be advised to attend the emergency department.
- For emotional or psychological distress disclosed during a study visit or interview, the interviewer will offer supportive listening, remind participants of their right to withdraw from the trial, offer to connect the participant with a study investigator, and refer participants back to their usual care provider.

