14. STATISTICAL AND ANALYTICAL METHODS

Our sample size calculation was intended to detect an HbA1c difference of 0.5%, presuming a standard deviation of HbA1c values at 3 months of 0.78% based on a recent similar trial of capillary blood glucose monitoring. To have 80% power to detect this HbA1c difference at a type 1 error rate of 5%, we would need 40 trial-completers in each arm. Given expected loss-to-follow-up rates of 20% or more, our enrollment target will be 100 participants.

Data will be analyzed according to intention-to-treat principles. Patients will be kept in the study group to which they were randomized, and efforts will be taken to ascertain outcome events in all patients randomized. Discontinuation of study treatment (isCGM) or no-show to CDE encounters are not equivalent to withdrawal from the study, and efforts will be made to contact study participants for HbA1c measurements and patient-reported outcomes at 12 weeks regardless.

Outcomes (HbA1c and patient-reported outcomes) are continuous scores – the difference at 12 weeks from baseline will be presented using simple means and standard deviations. On change in HbA1c, our primary outcome, we will test for a difference between intervention and enhanced usual care arms using linear regression with adjustment for age and sex. Secondary outcomes and diabetes-related distress will be analyzed in similar fashion, including follow-up values for patient-reported outcomes obtained at 6 and 12 weeks. Safety outcomes are dichotomous (e.g.: ED visits), and differences between trial arms will be assessed using Fisher's exact test. The primary outcome will be considered statistically significant at $p < 0.05$. Secondary and safety outcomes are considered hypothesis-generating and will also be considered statistically significant at $p < 0.05$. No correction for multiple comparisons is planned *a priori*. If the primary outcome is statistically significant at $p < 0.05$, the Benjamini-Hochberg procedure will be performed on secondary outcomes targeting a false discover rate of 20%, if requested by reviewers.

Secondary analyses are planned, and include:

- Post-hoc analysis of outcomes in clinically relevant groups, e.g.: by sex, baseline self-management empowerment, etc., using the above methods.

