APPENDIX 4: Instructions to Terminate LibreView Data Sharing

APPENDIX 5: Case Report Forms

Electronic case report forms with the following content

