Appendix 5.2: Baseline visit

Patient study ID

Baseline visit date

Patient demographics

- Age
- Sex
- Ethnicity (White, Asian, Black, Latin American, Arab, Indigenous (including Metis or First Nations))
- Marital status
- Income quintile (pre-tax: < \$36,500, \$36,500-<\$62,000, \$62,000-<\$92,000, >=\$92,000, refuse answer)
- Smoking status

Medical conditions

- Hypertension
- Dyslipidemia
- Heart disease
- Heart attack
- Heart failure
- Atrial fibrillation
- Stroke or TIA
- Peripheral artery disease
- COPD
- Asthma

Diabetes-related quantities

- Duration of diabetes
- Retinopathy (problem with the back of your eye that you were told was due to diabetes?)
- Diabetic nerve disease (problem with loss of sensation or with nerve pain that you were told was due to diabetes?)
- Foot infection without ulcer (an infection in your foot that you were told was due to diabetes?)
- Foot ulcer (a wound or hole in your foot that you were told was due to diabetes?)
- Amputation
- Chronic kidney disease (defined as eGFR <= 60 mL/min/1.73m² or UACR >= 3 mg/mmol or UPCR >= 15 mg/mmol or semi-quantitative urine dipstick >= 1+)
- Most recent eGFR on NetCare (date)
- Most recent proteinuria indicator on NetCare (date)
 - UACR
 - UPCR
 - Semi-quantitative urine dipstick proteinuria
- Previous use of fingerstick blood sugar measurement

Physical parameters

- BP
- Height (cm)

- Weight (kg)
- BMI (kg/m²)

Medication list

- Medication names, total daily dose
- Medication compliance: Frequency of missed doses (0%, 1-20%, 21-50%, > 50%)

Health care utilization

- ED visits in the last 6 months
- Hospital admission in the last 6 months
- Family physician visits in the last 6 months
- Diabetes specialist visits in the last 6 months

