Appendix 5.3: Follow-up visit

Patient study ID

Follow-up visit date

Diabetes-related quantities

- Retinopathy (problem with the back of your eye that you were told was due to diabetes?)
- Diabetic nerve disease (problem with loss of sensation or with nerve pain that you were told was due to diabetes?)
- Foot infection without ulcer (an infection in your foot that you were told was due to diabetes?)
- Foot ulcer (a wound or hole in your foot that you were told was due to diabetes?)
- Amputation
- Most recent eGFR on NetCare since baseline visit (date)
- Most recent proteinuria indicator on NetCare since baseline visit (date)
 - UACR
 - UPCR
 - Semi-quantitative urine dipstick proteinuria
- Use of fingerstick blood sugar measurement since baseline visit
 - Number of weeks using fingerstick blood sugar measurement
 - Number of fingerstick blood sugar measurements per day while using it
- Use of isCGM
 - Number of sensors since baseline visit
 - Number of scans per day (self-report) while sensor active

Adverse events

- Any adverse event that might be related to diabetes, diabetes treatment, or glucose monitoring (open adverse event reporting form)
- Skin reactions related to CGM
 - Type of skin reaction: Hives, dermatitis, bleeding
 - Able to continue using CGM?
 - Any treatment applied?
 - Barrier film
 - Steroid cream
 - Other

CDE compliance

- Number of CDE education and feedback sessions attended

Medications

- Medication names, total daily dose
- Any medication changes since baseline?
 - Number of new medications since baseline
 - Number of medications with dose increase since baseline
 - Number of discontinued medications since baseline
 - Number of medications with dose decrease since baseline
- Medication compliance: Frequency of missed doses (0%, 1-20%, 21-50%, > 50%)

Health care utilization

- ED visits since last study visit

- Hospital admission since last study visit
- Family physician visit since last study visit
- Diabetes specialist visit since last study visit

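### Three groups of secondary or safety outcomes do not match the data forms: physical measures, the CGM change score, and adverse events

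*Combined protocol and SAP*

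**What the plan says.** **Physical measures.** The Study Synopsis lists "Blood pressure, body weight, waist circumference, and patient-reported outcomes, measured as change in continuous score at 3 months compared to baseline". Section 13 adds: "We are performing in-person visits with participants to measure BP and weight". The synopsis follow-up row plans a "12-week in-person study encounter to complete study measurements". Section 10 names none of the three measures among its outcomes and refers to Appendix 5 for other variables. Appendix 5 is introduced as "Electronic case report forms with the following content". The baseline form (Appendix 5.2) has a block headed "Physical parameters" with blood pressure, height, weight and BMI. The form headed "Appendix 5.3: Follow-up visit" has no such block. Section 14 says "Outcomes (HbA1c and patient-reported outcomes) are continuous scores" and analyses secondary outcomes in the same way as the primary.

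**CGM measures.** For the isCGM arm only, Section 10 lists "change in time-in-target range, coefficient of variation, and glucose management indicator at 12 weeks compared to baseline". Section 6 has the first sensor started with staff help at the baseline visit and supplies three 14-day sensors, described as six weeks of monitoring. The synopsis gives the intervention 6 to 8 weeks and lets participants in this arm fund extra sensors. Appendix 5.5 records metrics for the first and the final fortnight of sensor wear, with a start date for each.

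**Adverse events.** The synopsis and Section 10 promise any adverse event, and Section 10 has investigators judge attribution afterwards. Appendix 5.6 includes a category for events not related to study treatment. The Appendix 5.3 prompt asks only about events that might be related to diabetes, its treatment or glucose monitoring.

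**The concern.** Appendix 5 is the plan's data specification: Section 10 says that its forms will be turned into the electronic ones. An outcome with no field there may have no place in the database.

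- **Physical measures.** If the forms are followed as written, no change in waist can be calculated, and a baseline waist that was not taken cannot be recovered. Blood pressure and weight could be measured at 12 weeks with nowhere to record them.
- **CGM.** A change between two periods of sensor wear would be reported as a 12-week change from baseline. The reference period is already on treatment: the participant can see the readings, and the first educator encounter falls in weeks 1-2.
- **Adverse events.** Relatedness would be screened at an open-label interview, before the investigators judge it. Section 14 compares safety outcomes between arms with Fisher's exact test, so what enters the count matters.

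**Working it through.** **1. Physical measures: outcomes against form fields**

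| Measure | Synopsis outcome | Section 10 outcome | Planned in Section 13 | Appendix 5.2 (baseline) | Appendix 5.3 (follow-up) |
|---|---|---|---|---|---|
| Blood pressure | yes | no | yes | yes | no |
| Weight | yes | no | yes | yes | no |
| Waist | yes | no | no | no | no |

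Appendix 5.2 has four physical fields and Appendix 5.3 has none. Waist has a field on 0 of the 2 visit forms and is not mentioned outside the synopsis in the available text (Figure 1 is not shown).

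**2. CGM: timing of the two windows**

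Inputs: 3 sensors of 14 days each (Section 6); intervention of 6 to 8 weeks (synopsis); final visit at 12 weeks, 12 × 7 = day 84.

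The plan's own figure first: 3 × 14 = 42 days, and 42 / 7 = 6 weeks, as Section 6 states.

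The first window is days 0-14, with midpoint day 7.

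| | Back-to-back wear | Wear spread over 8 weeks |
|---|---|---|
| Last day of wear | 42 | 8 × 7 = 56 |
| Last window | days 28-42 | days 42-56 |
| Midpoint of last window | 35 | 49 |
| Distance between midpoints | 35 − 7 = 28 days | 49 − 7 = 42 days |
| Share of 84 days | 28 / 84 = 1/3 | 42 / 84 = 1/2 |
| End of last window before day 84 | 84 − 42 = 42 days | 84 − 56 = 28 days |

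The second column assumes that the three sensors are worn with gaps and that the third ends at week 8. Self-funded sensors could move the last window later, up to day 84 if worn until the visit. That upper limit is an assumption, and Appendix 5.5 does not say whether such sensors count. In every case the first window lies after the sensor starts, so there is no pre-intervention CGM value.

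**3. Adverse events: what each place collects**

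- Synopsis and Section 10: any event, serious or not, with attribution judged later.
- Appendix 5.6: related and unrelated events can both be entered.
- Appendix 5.3 prompt, which opens the Appendix 5.6 form: possibly related events only.
- Captured separately: ED visits and admissions for any reason (Section 10, from interview and NetCare) and skin reactions (Appendix 5.3).

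The exposed group is therefore unrelated events that led to no ED visit or admission. The documents give no rate for these, so no count can be estimated.

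**The case against.** The strongest reply is that these are drafting slips. The intent to measure blood pressure and weight is explicit in Section 13 and in the synopsis follow-up row. Appendix 5 only lists content, and the built electronic forms are not visible. Section 10 defers to Appendix 5 for other variables, where blood pressure and weight do appear at baseline. Section 14 covers secondary outcomes by analogy with the primary, so an analysis method is not lacking. All of this stands. A reader might infer that 12-week blood pressure and weight will not be collected; the documents do not support that. They show only that the specification lacks the fields. For waist there is no comparable evidence of intent beyond the synopsis.

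On CGM, Appendix 5.5 already defines usable windows with dates, and the outcome is confined to one arm. That stands too: the fault is in the label, not in the data collected. It might also be tempting to require a minimum duration of wear. Nothing in the inconsistency calls for this, and it would select participants on behaviour after randomization.

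On adverse events, Section 10 sets an interview about any event, and Appendix 5.6 can hold unrelated ones, so a careful interviewer could still record them. A reader might cite the Appendix 5.6 definition, which needs no causal link, as decisive. It is weak support, because it is worded for recipients of a pharmaceutical product and this trial tests a device with education. The conflict rests instead on the synopsis and Section 10 against the Appendix 5.3 prompt, and there it remains.

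**Conclusion.** All three mismatches hold on the available text, as a minor point.

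- **Physical measures.** Follow-up blood pressure and weight have no field despite a clear plan to measure them. Waist has none at either visit.
- **CGM.** The label overstates the interval. With study-supplied sensors the midpoints are about 28 to 42 days apart, and the last window ends 42 to 28 days before day 84. The range rests on back-to-back wear at one end and wear spread over the synopsis's 8 weeks at the other, so neither one third nor one half of 84 days should be quoted alone.
- **Adverse events.** Unrelated events without an ED visit or admission could be missed if staff follow the prompt literally.

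It would be wrong to infer a threat to the trial's main conclusion. HbA1c has its own form at baseline and 12 weeks, and the patient-reported outcomes have theirs. The sample size does not depend on any of these items. No between-arm comparison uses the CGM outcome, and Section 14 treats secondary and safety outcomes as hypothesis-generating. The conclusion assumes that neither Figure 1 nor the built forms already supply the missing fields.

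**What to change.** 1. Add blood pressure and weight to Appendix 5.3. Either add waist to Appendices 5.2 and 5.3 or delete it from the synopsis. Make the Section 10 list agree.
2. In Section 10, relabel the CGM outcome as a descriptive, within-arm, on-treatment change from the first to the final two weeks of sensor wear. State whether self-funded sensors count. Report the actual timing of the windows from the dates already on Appendix 5.5. No minimum-wear exclusion is needed.
3. Change the Appendix 5.3 prompt to ask for any adverse event since baseline, and leave relatedness to the investigator review in Appendix 5.6.

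The cost is a few form fields and some wording. The 12-week visit is already in person with blood pressure and weight planned, so waist is the only added measurement, at two visits, and only if it is kept. Recording unrelated minor events adds a little interview and form time. The CGM statement becomes more modest, but no data are lost.

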1. OVERVIEW OF STUDY DESIGN

Figure 1: Overview of Study Design

2. INTRODUCTION AND RATIONALE

Glycemic control is an important treatment target for adults with diabetes.¹ Though rates of adults meeting glycated hemoglobin (HbA1c) targets of <= 7.0-7.5% have probably improved in the last decade, a large proportion of adults do not achieve their glycemic targets,²⁻⁵ for a variety of reasons.⁶

Self-monitoring of blood glucose can help adults with type 2 diabetes (T2DM) progress towards their glycemic targets.⁷ Continuous glucose monitoring (CGM), an alternative to traditional capillary blood glucose, uses a wearable sensor that continuously samples interstitial fluid glucose. Real-time CGM (rtCGM) continuously transmits blood glucose values, while intermittently scanned CGM (isCGM) requires scanning of the sensor to obtain the cumulated readings. CGM is painless, provides information on glucose trends, and has consistently demonstrated improved patient satisfaction compared to CBG, which tends to be limited by its “snap-shot” one-time perspective, and the inconvenience and discomfort associated with fingersticks.^{8,9}

While rtCGM has demonstrated effectiveness in reducing HbA1c compared to traditional capillary blood glucose monitoring, in adults with T2DM on insulin,¹⁰⁻¹³ the lower monthly cost of isCGM (FreeStyle Libre \$180)¹⁴ compared to rtCGM (Dexcom G6 \$395)¹⁵ makes isCGM an attractive alternative. However, the evidence for isCGM in T2DM is limited.¹⁶ Several cohort studies have shown improved HbA1c in adults initiating isCGM, but these studies are limited by lack of relevant comparators.¹⁷⁻²⁰ Only two trials have examined isCGM in T2DM. In the REPLACE study of adults on insulin, no difference was detected in HbA1c between isCGM and CBG groups at 6 months, though isCGM participants had lower time in hypoglycemia and higher treatment satisfaction.²¹ Yaron et al., randomized adults on prandial insulin and found a statistically significant 0.5% greater improvement in HbA1c in isCGM participants.²² The reason for the contrasting results may be related to the absence of structured one-on-one diabetes educator interactions in REPLACE; a previous study of adults with type 1 and type 2 diabetes has shown the importance of education in potentiating the effect of isCGM.²³ Overall, the effectiveness of isCGM at reducing HbA1c in T2DM remains unresolved.

Adults with “earlier diabetes”, i.e.: on non-insulin therapy only, comprise the majority of adults with T2DM. Yet, they are underrepresented in the current CGM literature.²⁴ Because their hypoglycemia risk and their opportunities for day-to-day medication adjustments are lower compared to adults on multiple daily doses of prandial insulin, it has been more challenging to demonstrate the value of glucose monitoring among these individuals.²⁵⁻²⁷ However, capillary blood glucose studies have shown that glucose self-monitoring can improve lifestyle and accelerate medication intensification, leading to lower HbA1c compared to usual 3-monthly HbA1c-driven care, in those with diabetes not on insulin therapy.²⁸⁻³¹ Some trials of rtCGM have examined this sub-population of T2DM and found benefit.^{10,12} For example, Vigersky et al. randomized adults with T2DM *not* on prandial insulin to intermittent use of rtCGM (2 weeks on, 1 week off) for 3 months versus CBG only. This trial showed reduced HbA1c in the intermittent rtCGM group at 3 months, that persisted up to 12 months, long after the intervention had stopped.¹³ Given the expense of CGM, intermittent sensor deployment is an important cost-

savings measure applicable to the real world use of CGM. Neither of the two trials of isCGM in T2DM, above, have examined this subpopulation, leaving the effectiveness of isCGM in earlier T2DM largely unknown.

